- Appendix IV New York Heart Association (NYHA) Class III
- Appendix V Blank
- Appendix VI Inhibitors and Inducers of CYP3A4
- Appendix VII Adverse Events Reported
- Appendix VIII Table 78-80 – Adverse Reactions/Organ Class

Study Schema

If a patient is deemed ineligible or a cancel, please refer to Section 13.0 for follow-up information.

¹ Cycle length=28 days

Generic name: Pazopanib
Mayo abbreviation: 786034
Availability: Novartis

1.0 Introduction

1.1 Renal Cell Carcinoma

Renal cell carcinoma (RCC) is a non-homogenous collection of histologically distinct tumor types broadly classified as clear cell and non-clear cell kidney cancer as recognized by the Heidelberg classification system. While clear cell histology forms the bulk (75-80%) (Cohen and McGovern 2005) of all kidney cancers several distinct non clear cell histological subtypes constitute 15-25% of all renal cell cancers. The approximate distribution among histological sub-types of kidney cancer is as follows:

Clear cell (75 to 85 percent of tumors)

Chromophilic (papillary) (10 to 15 percent)

Chromophobic (5 to 10 percent)

Oncocytic (uncommon)

Collecting duct (Bellini's duct) (very rare)

The genetic and molecular biology of clear cell renal cancer has been successfully targeted with the approval of several new drugs that inhibit the vascular endothelial growth factor (VEGF) and the mammalian-target of rapamycin (m-TOR) pathways since 2006 (Di Lorenzo, Autorino et al. 2009). These pathways are up regulated as a result of mutational inactivations in the Von Hippel-Lindau (VHL) gene that inhibition of these pathways using pazopanib (LaPlant and Louzon), sunitinib (Motzer, Hutson et al. 2007), sorafenib (Escudier, Eisen et al. 2007), everolimus (Motzer, Escudier et al. 2008), bevacizumab with interferon (Rini, Halabi et al. 2008) and temsirolimus (Hudes, Carducci et al. 2007) has resulted in slowing disease progression and prolonging longevity of life in the metastatic setting compared to previous cytokine based approaches for progressive stage IV disease.

Most of the above trials however excluded non clear cell histological subtypes, and it remains unclear if patients with metastatic non clear cell histology will derive therapeutic benefit from the above drugs as well, since the genetic and molecular characteristics of non clear cell histology are distinct and the clinical behavior of these histological subtypes are different from clear cell histology. For example, when initially diagnosed in the localized stage, papillary, chromophobe and oncocytomas have a better prognosis than clear cell renal cancer. However, after developing metastases, in general the survival of patients with non clear cell RCC becomes universally poor. The exception is collecting duct cancers (including medullary) of the kidney, which are extremely aggressive and carry a poor prognosis in any stage of detection.

At the molecular and genetic level the characteristics of non clear cell vary with histology. Papillary RCC, the second most common histological subtype is histologically categorized into Type I and Type II. Type I (sporadic and hereditary forms) is associated with activating mutations of the methyl-nitroso-nitroguanidine-induced (MET) oncogene on the long arm of chromosome 7 (Dharmawardana, Giubellino et al. 2004). These mutations result in ligand independent activation of intracytoplasmic tyrosine kinase domains, which constitutively activate hepatocyte growth factor (HGF)/MET pathway. Additionally in its

hereditary form families with Type I papillary RCC have germline mutations in MET oncogene which are passed on to offspring with variable penetrance. Individuals with these mutant alleles phenotypically present with bilateral multifocal papillary Type I RCCs (Sudarshan and Linehan 2006). Papillary Type II RCC on the other hand can present in its hereditary form with leiomyomatosis (Hereditary leiomyomatosis with RCC-HLRCC) due to mutations in the Fumarate Hydratase (FH) gene which inactivate the gene leading to generation of a pseudo-hypoxic state characterized by the upregulation of hypoxia inducible factor (HIF) similar to that seen in the VHL pathway in clear cell RCC, albeit by a different mechanism (Isaacs, Jung et al. 2005).

The mechanisms underlying chromophobe histology are lesser understood, although an autosomal dominant hereditary cancer syndrome, Birt-Hogg-Dube (BHD) syndrome associated with bilateral multifocal chromophobe RCC is the result of loss of folliculin protein is thought to interact with cellular activate mitogen protein kinase (cAMP) and m-TOR pathways (Nickerson, Warren et al. 2002). Apart from this mechanism, other mechanisms such as upregulation of cellular proto-oncogenic receptor tyrosine kinase (c-KIT) have also been observed in chromophobe RCC (Yamazaki, Sakamoto et al. 2003).

1.2 Clinical experience with VEGF axis inhibition in non clear cell histology

The underlying differences in molecular mechanisms for developing non clear RCC has a potential impact in therapeutic targeting, which resulted in excluding these histologies in the pivotal trials that targeted the VEGF axis with clear cell histology. However, with limitations there is some clinical evidence available indicative of efficacy for VEGF targeting in non clear cell RCC.

The Advanced Renal Cell Carcinoma Sorafenib Expanded Access Program, a non-randomized open label program initiated prior to drug approval treated 158 metastatic papillary RCC patients with sorafenib (Stadler, Figlin et al.). Stable disease was observed in 87 patients of 107 evaluable patients for 8 weeks with a partial response observed in an additional three patients.

In a multi-center, international, non-randomized open label compassionate use trial with sunitinib in poor prognosis populations that were excluded from other trials on the basis of brain metastasis, non clear cell histology, poor performance status and increased age, the overall survival of patients with non clear cell histology was observed to be improved (13.4 months compared to a historical control of 9.4 months) with an overall response rate of 11% for non clear histology (Gore, Szczylik et al. 2009).

Other small retrospective series have reported variable efficacy with sunitinib and sorafenib (Choueiri, Plantade et al. 2008) in patients with metastatic non clear histology with response rates ranging between 5% and 17% while recently a lack of response to sunitinib in 23 patients with metastatic papillary RCC was observed (Plimack E. et al. 2010 J Clin Oncol 28: 15s, 2010 (suppl; abstr 4604)) in a small phase II trial with a best response of 1.6 months in 8 patients demonstrating stable disease.

1.3 Clinical Experience with non VEGF axis inhibition strategies

Experience with non-VEGF axis directed drugs in non clear RCC has also been limited. In the Global Advanced RCC trial comparing temsirolimus, interferon or both for advanced

RCC, (Hudes, Carducci et al. 2007) 124 subjects (20%) had non clear RCC histology. In an exploratory analysis hazard ratios for over all survival among non clear RCC patients favored treatment with temsirolimus compared to interferon or observation. A prospective phase II trial of everolimus in advanced papillary RCC is currently ongoing in Europe and results remain unknown. A new novel oral receptor tyrosine kinase inhibitor, foretinib (formerly known as GSK 1363089/XL880) that targets c-MET and VEGFR-2 has been evaluated in an efficacy trial in advanced papillary RCC with interim data on the first 60 patients recently reported in abstract form (SrinivasinR, et al. J Clin Oncol 27:15s, 2009 (suppl; abstr 5103)). Of the 35 evaluable pts, 4 patients had confirmed partial response and 27 had stable disease as best response with 6 patients ≥ 12 months, 3 patients ≥ 9 months and 3 patients ≥ 6 months. Four of 5 patients with Hereditary Papillary RCC had shrinkage (15-53%) in all measurable tumors while twenty-three patients with sporadic Papillary RCC had shrinkage (2-58%) in the sum of measurable tumors. Other trials with single agent erlotinib in advanced stage papillary RCC (Gordon, Hussey et al. 2009) or in combination with bevacizumab are currently underway at the National Institute of Health.

Cytotoxic chemotherapy has so far yielded poor efficacy results in non-clear-cell renal cell carcinoma (RCC). A phase II study conducted to assess the efficacy of carboplatin and paclitaxel in such patients observed a response rate of 0% with a median survival of 63 weeks (Bylow, Atkins et al. 2009). In another phase II multi-center trial that tested gemcitabine and cisplatin in collecting duct tumors in 23 patients found a response rate of 26% with a progression free survival of 7.1 months (compared to historical controls) and an overall survival of 10.5 months with considerable toxicity (Oudard, Banu et al. 2007).

1.4 Mayo Clinic Nephrectomy database experience with non clear cell renal cell cancer

At the Mayo Clinic (Rochester), (Department of Urology) an active kidney tumor registry has been maintained since 1970. The Nephrectomy Registry is currently complete with clinical follow up through 2007 and provides a rich source of clinical outcomes based on various histological subtypes. Between 1970 and 2007, 3714 nephrectomies for RCC were performed that had a specific RCC histo-path subtype with a breakdown as follows:

3051 clear cell RCC

499 papillary RCC

156 chromophobe RCC

8 collecting duct RCC

(Sarcomatoid differentiation can arise in all of these subtypes and is not considered a separate subtype according to the AJCC classification)

Among the 663 nephrectomies for non-clear cell RCC, 26 were M1 at nephrectomy and 48 subsequently developed metastases sometime following nephrectomy. For the 74 cases with distant metastases either at nephrectomy or following nephrectomy, the overall survival rates at 1, 3, and 5 years following distant metastases were 55.2%, 24.9%, and 16.3%, respectively (Leibovich, Lohse et al.). Non-clear cell metastatic RCC survival

reported from another large kidney cancer database from Memorial Sloan Kettering, published by Motzer et al (Motzer, Bacik et al. 2002) also provides insight into the poor prognosis of these histological subtypes. Of the 64 patients followed between 1985 and 2001, the median survival of metastatic non clear cell RCC was found to be 9.4 months, with survival longer for patients with chromophobe tumors than with collecting duct and papillary cancers. Patients in this review had received cytokine and or hormonal treatments with negligible responses highlighting an unmet need for the treatment in this group of patients.

Mayo Clinic (Rochester) annually averages 4-6 metastatic non-clear cell RCCs that undergo nephrectomy with a similar incidence at Mayo Clinic, Florida and Arizona. In addition in the Medical Oncology division at Rochester between 3 and 7 metastatic non-clear cell RCCs are treated annually.

Since the role of active treatment agents in metastatic RCC of non-clear-cell histologies remains to be established and the efficacy of pazopanib in delaying disease progression in metastatic clear cell RCC is unknown in non clear cell histological sub types, the current prospective phase II trial is designed to evaluate the efficacy of pazopanib in advanced stage non clear RCC patients.

1.5 Pazopanib Information

Angiogenesis, the process of new blood vessel formation, plays an important role in the development of malignancy as well as the growth and progression of metastatic lesions. The molecular pathways involved in angiogenesis have been targeted for anti-tumor therapy. Numerous growth factors and cytokines are involved in the angiogenic process. Among these factors, vascular endothelial growth factor (VEGF) has a predominant role as a central mediator of tumor-related angiogenesis, and its expression has been shown to be an adverse prognostic factor for a number of solid tumors [Folkman, 1971; Folkman 1997; Ferrara, 1997].

$\alpha\beta$

GW786034 (pazopanib) is an orally-bioavailable, adenosine triphosphate (ATP)-competitive tyrosine kinase inhibitor (TKI) of vascular endothelial growth factor (VEGF) receptor (VEGFR)-1, -2, and -3, platelet-derived growth factor receptor (PDGFR)- α and β , and stem cell growth factor receptor (c-Kit) [Kumar, 2007]. Pazopanib administered as oral doses up to 800 mg daily is being developed for the treatment of a variety of cancers and is currently approved by the Food and Drug Administration (FDA; New Drug Application #022465), European Medicines Agency (EMA) and other regulatory authorities as a monotherapy treatment for patients with advanced renal cell carcinoma (RCC) and advanced soft tissue sarcoma (STS). GW786034 is hereafter referred to as pazopanib in this document.

Nonclinical pharmacology studies conducted in vitro and in vivo have shown that pazopanib is a potent and selective orally bioavailable, adenosine triphosphate competitive, TKI of VEGFR-1, -2, and -3; PDGFR- α and - β ; and c-Kit. Pazopanib was generally efficacious in oral dosing xenograft models and in angiogenesis and neovascularization models using oral and topical (skin and ocular dosing) administration.

As of 09 September 2015, a total of 53 GlaxoSmithKline (GSK)-sponsored studies of pazopanib have been conducted in oncology indications (including 2 studies initiated by

National Cancer Institute [NCI] VEG110827/NCI8063 and PZP114411/ADVL0815). There is 1 ongoing clinical study in Hereditary Hemorrhagic Telangiectasia (HHT). Ten GSK-sponsored studies have been conducted in ophthalmic indications, and 1 GSK-sponsored study has been conducted in subjects with psoriasis.

Cumulatively, as of 09 September 2015, approximately 8557 patients and healthy volunteers were enrolled and treated in pazopanib clinical studies, of whom 5909 received pazopanib as monotherapy or in combination with other hemotherapeutic agents. Data collected to date show that pazopanib administration at 800 mg daily is associated with a reasonable safety profile and encouraging efficacy in various oncology settings.

In VEG110727 (a randomized placebo-controlled Phase III study of pazopanib monotherapy in subjects with STS), the median time on pazopanib was 19.4 weeks, as compared with 8.1 weeks in the placebo arm. The most common AEs ($\geq 20\%$) reported in the pazopanib arm (as of 29 Mar 2013) were fatigue (65%), diarrhea (59%), nausea (56%), weight decreased (51%), hypertension (42%), decreased appetite (40%), hair color changes (39%), vomiting (34%), tumor pain (30%), dysgeusia (28%), gastrointestinal pain (24%), headache (24%), musculoskeletal pain (23%), myalgia (23%), and dyspnea (20%). Twenty-eight percent of subjects on placebo and 63% of subjects on pazopanib experienced an AE of maximum Grade 3 or higher. The proportion of subjects who experienced maximum Grade 4 and Grade 5 AEs was similar in both treatment arms.

In VEG110655 (a randomized, placebo-controlled, Phase III study of pazopanib monotherapy in subjects with ovarian, fallopian tube or primary peritoneal cancer), the mean time on study drug in the pazopanib arm was shorter than in the placebo arm (8.9 months vs. 11.7 months). The most common AEs ($>20\%$) occurring in subjects in the pazopanib arm included hypertension (54%), diarrhea (53%), nausea (37%), headache (29%), fatigue (28%), and neutropenia (22%). A higher proportion of subjects in the pazopanib arm had Grade 3 or Grade 4 AEs compared with the placebo arm (63% vs. 23%); the majority of these events were Grade 3. The most common Grade 3 AEs ($\geq 5\%$) in the pazopanib arm included hypertension (29%), diarrhea (8%), neutropenia (6%) and ALT increased (5%). Fatal SAEs were reported in 3 subjects in the pazopanib arm and 1 subject in the placebo arm.

An analysis of integrated safety data from VEG110655 and VEG114012 (a randomized, placebo-controlled, Phase II study of pazopanib monotherapy in East Asian women with ovarian, fallopian tube or primary peritoneal cancer) showed a safety profile similar to that observed in the pazopanib arm of VEG110655 alone. Adverse events that occurred in at least 20% of pazopanib-treated subjects in the integrated analysis included: hypertension (57%), diarrhea (52%), nausea (34%), fatigue (27%), headache (27%), neutropenia (27%), hair color changes (23%), and ALT increased (20%). Of the most common AEs in pazopanib-treated subjects, the incidences of diarrhea, nausea, and fatigue in the ovarian studies were similar or lower compared with those in the integrated STS and RCC studies, as well as in RCC Study VEG108844. Hypertension and neutropenia occurred more frequently in pazopanib-treated subjects in the ovarian studies.

A number of these events are known class effects of VEGF inhibitors. Therefore, this protocol is designed to closely monitor and provide clear management guidelines for these events based on the clinical experience with pazopanib to date.

2.0 Goals

2.1 Primary

2.11 To determine the efficacy of pazopanib in non clear cell metastatic renal cell cancer patients as assessed by the overall survival rate at 12 months.

2.2 Secondary

2.21 To determine the rates of best tumor response at the end of the first two treatment cycles of pazopanib in non clear cell metastatic renal cell cancer patients.

2.22 To determine the benefit of pazopanib in increasing progression free survival time.

2.23 To describe toxicity profile of pazopanib in non clear cell metastatic renal cell cancer patients.

3.0 Patient Eligibility

3.1 Inclusion Criteria

3.11 Age \geq 18 years

3.12 Histological confirmation of non-clear cell renal cancer (including Chromophilic (papillary), Chromophobic, Oncocytic, sarcomatoid, Collecting duct (Bellini's duct), translocation-type carcinoma or medullary renal cell carcinoma.

3.13 Up to one prior treatment for metastatic non clear cell carcinoma is allowed prior to registration as long as the agent used to treat was not pazopanib.

3.14 Measurable or non-measurable metastatic disease as defined in Section 11.0.

3.15 ECOG Performance Status (PS) 0, 1 or 2 (Appendix II).

3.16 The following laboratory values obtained \leq 14 days prior to registration.

- ANC \geq 1500
- PLT \geq 100,000
- HgB $>$ 9.0 g/dL. NOTE: Subjects may not have had a transfusion within 7 days of registration.)
- Total Bilirubin $<$ 1.5 x ULN
- Alanine amino transferase (ALT) \leq 2.5 X ULN. NOTE: Concomitant elevations in bilirubin and ALT above 1.0 x ULN (upper limit of normal) is not permitted.

- Aspartate aminotransferase (AST) $\leq 2.5 \times$ ULN. Note: Concomitant elevations in bilirubin and AST above $1.0 \times$ ULN (upper limit of normal) is not permitted.
- Urine Protein to Creatinine Ratio (UPC; appropriate appendix) (UPC) < 1
NOTE: If UPC ≥ 1 , then a 24-hour urine protein must be assessed. Subjects must have a 24-hour urine protein value < 1 g to be eligible.
- Prothrombin time (PT) or international normalized ratio (INR) $\leq 1.2 \times$ ULN NOTE: Subjects receiving anticoagulant therapy are eligible if their INR is stable and within the recommended range for the desired level of anticoagulation

3.17 A female is eligible to enter and participate in this study if she is of:

a. Non-childbearing potential (i.e., physiologically incapable of becoming pregnant), including any female who has had:

- A hysterectomy
- A bilateral oophorectomy (ovariectomy)
- A bilateral tubal ligation
- Is post-menopausal

Subjects not using hormone replacement therapy (HRT) must have experienced total cessation of menses for ≥ 1 year and be greater than 45 years in age, OR, in questionable cases, have a follicle stimulating hormone (FSH) value > 40 mIU/mL and an estradiol value < 40 pg/mL (< 140 pmol/L).

Subjects using HRT must have experienced total cessation of menses for ≥ 1 year and be greater than 45 years of age OR have had documented evidence of menopause based on FSH and estradiol concentrations prior to initiation of HRT

b. Childbearing potential, including any female who has had a negative serum pregnancy test, ≤ 7 days prior to registration.

c. Agrees to use adequate contraception. Acceptable contraceptive methods, when used consistently and in accordance with both the product label and the instructions of the physician, are as follow:

- Complete abstinence from sexual intercourse for 14 days before exposure to investigational product, through the dosing period, and for at least 21 days after the last dose of investigational product
- Oral contraceptive, either combined or progestogen alone
- Intrauterine device (IUD) or intrauterine system (IUS) with a documented failure rate of less than 1% per year
- Male partner sterilization (vasectomy with documentation of azoospermia) prior to the **female subject's entry** into the study, and this male is the sole partner for that subject
- Double barrier method: condom and an occlusive cap (diaphragm or cervical/vault caps) with a vaginal spermicidal agent (foam/gel/film/cream/suppository)

- 3.18 Subjects must provide written informed consent prior to performance of study-specific procedures or assessments, and must be willing to comply with treatment and follow-up. Procedures conducted as part of the subject's routine clinical management (e.g., blood count, imaging study) and obtained prior to signing of informed consent may be utilized for screening or baseline purposes provided these procedures are conducted as specified in the protocol.
- 3.19 Willing to return to Mayo Clinic enrolling institution for follow-up.
- 3.2 Exclusion Criteria
- 3.21 Any of the following because this study involves an investigational agent whose genotoxic, mutagenic and teratogenic effects on the developing fetus and newborn are unknown
- Nursing women
 - Pregnant women
 - Men or women of childbearing potential who are unwilling to employ adequate contraception
- 3.22 Co-morbid systemic illnesses or other severe concurrent disease which, in the judgment of the investigator, would make the patient inappropriate for entry into this study or interfere significantly with the proper assessment of safety and toxicity of the prescribed regimens.
- 3.23 Immunocompromised patients (other than that related to the use of corticosteroids) including patients known to be HIV positive.
- 3.24 Prior history of receiving pazopanib treatments.
- 3.25 Uncontrolled intercurrent illness including, but not limited to:
- ongoing or active infection,

 - History of abdominal fistula, gastrointestinal perforation, or intra-abdominal abscess ≤ 28 days prior to registration.
 - Clinically significant gastrointestinal abnormalities that may affect absorption of investigational product including, but not limited to:
 - Malabsorption syndrome
 - Major resection of the stomach or small bowel.
- 3.29c Corrected QT interval (QTc) > 480 msec using Bazett's formula.
- 3.29d Receiving any medications or substances with risk of torsades de pointes (see Appendix II). Note: medications or substances on the list "Drugs with Risk of Torsades de Pointes" are prohibited. Medications or substances on the list "Drugs with Possible or Conditional Risk of Torsades de Pointes" may be used while on study with extreme caution and careful monitoring.
- 3.29e Known endobronchial lesions and/or lesions infiltrating major pulmonary vessels and/or hemoptysis in excess of 2.5 mL (or one half teaspoon) ≤ 8 weeks of registration
- 3.29f Treatment with any of the following anti-cancer therapies: radiation therapy, surgery or tumor embolization, chemotherapy, immunotherapy, biologic therapy, investigational therapy or hormonal therapy ≤ 14 days prior to registration.
- 3.39g Prior autologous or allogeneic organ or tissue transplantation.
- 3.39h Elective or planned major surgery to be performed during the course of

the trial.

- 3.39i Receiving any medications or substances that are **strong or moderate inhibitors** of CYP3A4 (for a listing of medications or substances see Appendix VI).

Use of the following strong or moderate inhibitors are prohibited ≤ 7 days prior to registration.

- 3.39j Receiving any medications or substances that are **inducers** of CYP3A4 (for a listing of medications or substances see Appendix VI).

Use of inducers are prohibited ≤ 7 days prior to registration.

4.0 Test Schedule	Active Monitoring Phase					
	≤28 days prior to registration	≤14 days prior to registration	Day 1 ⁴ , Every cycle	On interval weeks 2, 6, 10	Every other cycle	End of treatment
Tests and procedures						
Informed Consent	X					
History and exam, Wt, PS			X			X
Adverse event assessment			X			
Height		X				
Pregnancy test		X ²				
Vital Signs, including temperature		X	X			X
Echo (2D M-Mode)	X ^R				X ⁸	
Hematology CBC with diff, platelets		X	X ^{R,6}			X
Chemistries ¹		X	X ^{R,6}	X ⁹		X
UPC Urine		X				
Thyroid Function Test (TSH)		X ^R			X ^R	
Coagulation Test: PT, PTT		X	X			
CT Head/MRI		X ^R				
CT scan of chest, abdomen or pelvis, MRI, etc		X ^R			X ⁷	
Bone Scan					X ⁵	
EKG		X ^R	X			
Medication Diary			X ³			

1. SGOT, SGPT, total bili, Na, K, Cl, CO₂, BUN, creatinine, LDH, hemoglobin, calcium, albumin, total protein, magnesium, phosphorus and alkaline phosphatase.
2. For women of childbearing potential, ≤7 days prior to registration.
3. The diary must begin the day the patient starts taking the medication and must be completed per protocol and returned to the treating institution OR compliance must be documented in the medical record by any member of the care team.
4. +/- 3 days
5. If applicable
6. Research funded, cycles 1 and 2 only
7. Use the same method throughout the study. Follow-up scans to be performed every other cycle (8 weeks). Repeat measurements are required 8 weeks following an objective Response. See Section 11.0 for full RECIST criteria.
8. Every 4 months while on study, sooner should clinical symptoms indicate. These follow-up echocardiograms will coincide with restaging visits.
9. SGOT, SGPT, total bili, only and can be done at study site or locally and faxed.
- R Research funded (see Section 19.0)

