APPENDIX II

Drugs with Risk of Torsades de Pointes

This list contains medications that are generally accepted (and documented in published data) as having an increased risk of QT prolongation and/or torsades de pointes. **Concomitant administration of pazopanib and a medication on this list is prohibited.**

Generic Name	Brand Name	Comments
Amiodarone	Cordarone®, Pacerone®	Low risk torsades de pointes
Arsenic trioxide	Trisenox®	Torsades de pointes
Bepidil	Vasocor®	
Chloroquine	Aralen®	
Chlorpromazine	Thorazine®	
Cisapride	Propulsid®	Restricted availability in U.S.
Clarithromycin	Biaxin®	
Disopyramide	Norpace®	Torsades de pointes
Dofetilide	Tikosyn®	Torsades de pointes
Dolasetron	Anzemet®	
Droperidol	Inapsine®	Torsades de pointes
Erythromycin	Erythrocin®, E.E.S. ®	IV > PO
Halofantrine	Halfan®	
Haloperidol	Haldol®	IV > PO, high doses increase QT prolongation and torsades de pointes
Ibutilide	Corvert®	Torsades de pointes, female > male, non-Caucasian > Caucasian
Levomethadyl	Orlaam®	
Mesoridazine	Serentil®	
Methadone	Dolophine®, Methadose®	
Pentamidine	Pentam®, Nebupent®	
Pimozide	Orap®	
Procainamide	Pronestyl®, Procan®, Procanbid®	N-acetylprocainamide causes torsade de pointes, not parent compound
Quinidine	Cardioquin®, Quinaglute®	Torsades de pointes
Sotalol	Betapace®	Torsade de pointes female > male
Sparfloxacin	Zagam®	
Thioridazine	Mellaril®	

Note: the above list is not all-inclusive.

References:

Kies SJ, Pabelick CM et al. Anesthesia for Patients with Congenital Long QT Syndrome. *Anesthesiology* 2005;102:204-210

Roden DM. Drug-Induced Prolongation of the QT Interval. *The New England Journal of Medicine* 2004;350:1013-1022.

<http://www.azcert.org/medical-pros/druginteractions.cfm> Accessed 5/13/11

Drugs with Possible or Conditional Risk of Torsades de Pointes

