This list contains medications that, in some reports, have been associated or weakly associated with causing torsades de pointes and/or QT prolongation. There is insufficient data that these medications alone may cause torsades de pointes and/or QT prolongation, however when pazopanib is given concomitantly with a medication on this list (or other risk factors are present such as bradycardia, electrolyte disturbances, congenital long QT syndrome, or concomitant drugs that inhibit metabolism), there may be possible or conditional risk of torsades de pointes and/or QT prolongation. **Extreme caution and careful monitoring should be instituted with concomitant administration of pazopanib and a medication on this list.**

Generic Name	Brand Name	Comments
Alfuzosin	Uroxatral®	
Amantadine	Symmetrel®	Low
Amitriptyline	Elavil®	Nonspecific ECG changes reported.
Atazanavir	Reyataz®	
Azithromycin	Zithromax®	
Chloral hydrate	Noctec®	
Ciprofloxacin	Cipro®	
Citalopram	Celexa®	
Clomipramine	Anafranil®	
Desipramine	Pertofrane®	QT prolongation, VF/sudden death reported
Diphenhydramine	Benadryl®, Nytol®	
Dolasetron	Anzemet®	Granisetron < Ondansetron < Dolasetron
Doxepin	Sinequan®	
Dronedarone	Multaq®	
Escitalopram	Lexapro®, Cipralex®	
Felbamate	Felbatrol®	
Flecainide	Tambocor®	
Foscarnet	Foscavir®	
Fosphenytoin	Cerebyx®	
Fluconazole	Diflucan®	IV > PO
Fluoxetine	Prozac®, Sarafem®	1 in 10,000 ventricular arrhythmias reported
Galantamine	Reminyl®	
Gatifloxacin	Tequin®	
Gemifloxacin	Factive®	
Granisetron	Kytril®	Granisetron < Ondansetron < Dolasetron
Imipramine	Norfranil®	Nonspecific arrhythmias reported
Indapamide	Lozol®	
Isradipine	Dynacirc®	
Itraconazole	Sporanox®	
Ketoconazole	Nizoral®	
Lapatinib	Tykerb®	
Levofloxacin	Levaquin®	Lower risk than that of similar agents
Lithium	Lithobid®, Eskalith®	

Moexipril/HCTZ	Uniretic®	
Moxifloxacin	Avelox®	
Nicardipine	Cardene®	
Nilotinib	Tasigna®	
Nortriptyline	Pamelor®	Nonspecific arrhythmias reported
Octreotide	Sandostatin®	
Ofloxacin	Floxin®	
Ondansetron	Zofran®	Granisetron<Ondansetron< Dolasetron
Oxytocin	Pitocin®	
Paliperidone	Invega®	
Paroxetine	Paxel®	Lower risk than TCA's
Perflutren lipid microspheres	Definity®	
Protriptyline	Vivactil®	
Quetiapine	Seroquel®	QT prolongation
Ranolazine	Ranexa®	
Risperidone	Risperdal®	QT prolongation, sudden death reported
Ritonavir	Norvir®	
Sertraline	Zoloft®	Lower risk than TCA's
Solifenacin	VESIcare®	
Sunitinib	Sutent®	
Tacrolimus	Prograf®	
Tamoxifen	Nolvadex®	
Telithromycin	Ketek®	

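### Appendix II lists dolasetron as both prohibited and usable with caution, so exclusion 3.29d gives two answers for that one drug

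*Combined protocol and SAP*

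**What the plan says.** Exclusion 3.29d bars patients receiving drugs that carry a risk of torsades de pointes and refers to Appendix II for the names. Its note sets a separate rule for each list there: drugs on the first list "are prohibited. Medications or substances on the list 'Drugs with Possible or Conditional Risk of Torsades de Pointes' may be used while on study", though that permission is tied to close monitoring.

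The Appendix II text repeats both rules. Above the first list: "Concomitant administration of pazopanib and a medication on this list is prohibited". Above the second: "Extreme caution and careful monitoring should be instituted with concomitant administration of pazopanib and a medication on this list".

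The first list contains the row "Dolasetron Anzemet", with an empty comment column. The second contains the row "Dolasetron Anzemet® Granisetron < Ondansetron < Dolasetron".

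**The concern.** The two lists carry different instructions, so they work only if no drug is on both. Dolasetron is on both.

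Two decisions are affected. At registration, a patient already taking dolasetron fails 3.29d by the first list and passes it by the second. On study, a clinician choosing an antiemetic is told by one list not to give dolasetron and by the other that it may be given with monitoring.

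The situation is a plausible one. In the RCC study summarised in Appendix VII, 26% of pazopanib patients had nausea and 21% had vomiting, and Section 9.1 leaves antiemetics to the attending physician. Section 15.17 classes QT prolongation as common and torsade de pointes as uncommon with pazopanib in RCC, which is the risk that the lists are there to manage.

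Eligibility also has a formal consequence. Section 13.5 makes a patient ineligible if any criterion was not met at registration, and Section 16.11 counts only eligible patients as evaluable. Two readers could class the same dolasetron user differently.

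**Working it through.** There is no sample size or power figure to reproduce here. The check compares the two lists and looks for a rule of precedence.

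**Step 1. Compare the two entries.**

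| | First list | Second list |
|---|---|---|
| Title | Drugs with Risk of Torsades de Pointes | Drugs with Possible or Conditional Risk of Torsades de Pointes |
| Rule in 3.29d | Prohibited | Allowed with caution and monitoring |
| Rule in Appendix II | Prohibited with pazopanib | Caution and monitoring with pazopanib |
| Dolasetron (Anzemet) row | Yes | Yes |
| Route or dose limit in that row | None | None |
| Comment in that row | None | "Granisetron < Ondansetron < Dolasetron" |

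The comments differ, so this is not one row repeated when the text was extracted. They are two separate entries.

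**Step 2. Count the overlap.** I counted the generic names in each list and took those common to both.

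- First list: 25 names.
- Second list: 64 names.
- Names on both: 1, dolasetron.
- Share of the first list: 1/25 = 4.0%.
- Share of the second list: 1/64 = 1.6%.

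These are shares of drug names. They say nothing about how many patients would take the drug.

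**Step 3. Look for text that settles it.**

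- 3.29d states both rules and gives no order between them.
- The Appendix II introductions do not mention a drug that is on both lists.
- Section 9.1 leaves antiemetics to the physician and does not mention the lists.
- Appendix VI does not name dolasetron among the CYP3A4 inhibitors or inducers, so 3.39i and 3.39j do not decide the matter.

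**Step 4. Check what limits harm if a site takes the permissive reading.**

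- 3.29c excludes patients with QTc above 480 msec.
- The test schedule in Section 4.0 has an EKG at screening and on Day 1 of every 28-day cycle.
- Sections 8.1 to 8.3 discontinue pazopanib at QTc of 500 msec or more.
- The permissive rule itself requires caution and monitoring.

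These safeguards reduce the consequence of a wrong reading. They do not tell a site which reading is right.

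**The case against.** The strongest reply is that a careful reader would reach the ban anyway, for three reasons.

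- The two rules are not symmetric. One forbids and the other only permits, so withholding dolasetron satisfies both.
- The caution list does not override bans elsewhere. Fluconazole, itraconazole, ketoconazole, ritonavir and telithromycin are on it, yet 3.39i with Appendix VI bars them as strong or moderate CYP3A4 inhibitors.
- The list definitions point the same way. The first covers drugs whose risk is accepted and documented; the second covers weaker or insufficient evidence. A drug that meets the first definition does not belong on the second list. The ranking comment appears on all three setron rows and puts dolasetron highest, so the row may have been meant only as a within-class comparison. That last point is an inference.

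Much of this stands. The ban is the safer and more sensible reading, this looks like a drafting slip, and there is always one compliant course of action.

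It does not remove the conflict. The CYP3A4 bar is a different criterion with a different purpose, so it does not set the order between two rules inside 3.29d. The definitions show that the overlap is an error, but a reader who looks the drug up only in the caution list finds it there with permission to use it. Nothing in that row points to the other list.

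**Conclusion.** The point holds, as a minor one. 3.29d and Appendix II give contradictory instructions for dolasetron, and the documents contain no rule that resolves them. The size is one drug, the only overlap between lists of 25 and 64 names. How many patients it could touch is unknown, because the documents give no figure for dolasetron use.

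The conclusion rests on the lists as printed. Appendix II says that neither is complete, so unlisted drugs were not considered. The definition of the primary endpoint, the sample size and the error rates are unaffected. What is affected is the eligibility and concomitant-medication rule for this one drug.

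**What to change.** Delete the dolasetron row from the list of drugs with possible or conditional risk. The drug then appears only on the prohibited list and 3.29d gives one answer. This agrees with the caution list's own comment, which ranks dolasetron above granisetron and ondansetron.

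The cost is the removal of one appendix row and the loss of one antiemetic option. Granisetron and ondansetron are on the caution list only and remain usable under its conditions. No visit, test, endpoint or analysis changes. A sentence in 3.29d saying that the prohibited list governs any drug on both would also work, but it would leave the misleading row in place.
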